6.2 STUDY RELATED BENEFITS

Because the surgery and all the follow-up visits are the same as if the subject would not participate in this study, there are no additional medical benefits associated with participating in this study. The information gained from this study may help improve the treatment of people in the future that need to undergo any of the procedures included in this study.

7. OBJECTIVE(S)

7.1 PRIMARY OBJECTIVE

The primary objective of this study is to assess the safety and performance post-market of the PEEK Anchors (DYNOMITE[®], SPYROMITE[®], RAPTORMITE[®], FOOTPRINT[®] ULTRA PK SL) in extremities over a time period of 6 months after intervention.

7.2 SECONDARY OBJECTIVE

The secondary objective of this study is to assess the safety and performance post-market of the PEEK Anchors (DYNOMITE[®], SPYROMITE[®], RAPTORMITE[®], FOOTPRINT[®] ULTRA PK SL) in extremities over a time period of 12 months after intervention.

8. STUDY PRODUCT(S)

8.1 DYNOMITE[®] 2.0 PK SUTURE ANCHOR WITH NEEDLES

The Smith & Nephew DYNOMITE[®] 2.0 PK Suture Anchor with Needles is a push/tap-in fixation device intended to provide secure attachment of soft tissue to bone. The device consists of a suture anchor with attached non-absorbable suture(s) and stainless steel needles preassembled

CONFIDENTIAL AND PROPRIETARY

This document contains information that is confidential and proprietary to Smith & Nephew PLC and Smith & Nephew, Inc. and is intended for use only by Smith & Nephew and its manufacturer. It shall not be reproduced or copied in whole or in part, nor shall the contents be disclosed by any means without prior written permission from Smith & Nephew, nor shall anyone make any use of it that is contrary to the expressed or implied wishes of Smith & Nephew.

Study Protocol—Device	
Safety and Performance of PEEK Anchors (DYNOMITE [°] , SPYROMITE [°] , RAPTORMITE [°] , FOOTPRINT [°] ULTRA PK SL) in Extremities	Number: 2018.15.SMD.PEEK.RET.EXT
	Version: 2.0 05Dec2018
	Page: Page 17 of 54

to an insertion device. The suture anchor is provided sterile, for single use only. DYNOMITE[°] 2.0 PK Suture Anchor with Needles contains: Non-absorbable suture anchor, 2.0 mm diameter – PEEK-OPTIMA[®] from Invibio[®] (polyetheretherketone), Insertion device – stainless steel shaft with ABS and polycarbonate handle. Non-absorbable suture(s) with attached stainless steel needles.

Non-absorbable suture options:

- White – braided, uncoated, UHMW polyethylene
- White/blue – braided, uncoated, UHMW polyethylene with monofilament polypropylene cobraid
- White/black – braided, uncoated, UHMW polyethylene with monofilament nylon cobraid
- Braided, silicone, or PTFE-impregnated polyester (USP), non-absorbable

8.2 RAPTORMITE[°] 3.0 SUTURE ANCHOR WITH NEEDLES

The Smith & Nephew RAPTORMITE[°] Suture Anchor is a fixation device intended to provide secure attachment of soft tissue to bone. The device consists of a suture anchor with attached non-absorbable suture(s) and stainless steel needles preassembled to an insertion device. The suture anchor is provided sterile, for single use only. RAPTORMITE[°] 3.0 Suture Anchor with Needles contains: non-absorbable suture anchor, 3.0 mm diameter – PEEK-OPTIMA[®] from Invibio[®] (polyetheretherketone), Insertion device – stainless steel shaft with ABS and polycarbonate handle. Non-absorbable suture(s) with attached stainless steel needles. Refer to individual suture anchor product labels for suture size and type, and quantity.

Non-absorbable suture options:

- White – braided, uncoated, UHMW polyethylene
- White/blue – braided, uncoated, UHMW polyethylene with monofilament polypropylene cobraid

CONFIDENTIAL AND PROPRIETARY

This document contains information that is confidential and proprietary to Smith & Nephew PLC and Smith & Nephew, Inc. and is intended for use only by Smith & Nephew and its manufacturer. It shall not be reproduced or copied in whole or in part, nor shall the contents be disclosed by any means without prior written permission from Smith & Nephew, nor shall anyone make any use of it that is contrary to the expressed or implied wishes of Smith & Nephew.

Study Protocol—Device	
Safety and Performance of PEEK Anchors (DYNOMITE [°] , SPYROMITE [°] , RAPTORMITE [°] , FOOTPRINT [°] ULTRA PK SL) in Extremities	Number: 2018.15.SMD.PEEK.RET.EXT
	Version: 2.0 05Dec2018
	Page: Page 18 of 54

- White/black – braided, uncoated, UHMW polyethylene with monofilament nylon cobraid
- White/green – braided, silicone-coated, polyester (USP), non-absorbable

8.3 SPYROMITE™ 2.0 PK SUTURE ANCHOR WITH NEEDLES

The Smith & Nephew SPYROMITE[°] 2.0 PK Suture Anchor with Needles is a screw-in fixation device intended to provide secure attachment of soft tissue to bone. The device consists of a suture anchor with attached non-absorbable suture(s) and stainless steel needles preassembled to an insertion device. The suture anchor is provided sterile, for single use only. SPYROMITE[°] 2.0 PK Suture Anchor with Needles contains: Non-absorbable suture anchor, 2.0 mm diameter – PEEK-OPTIMA® from Invibio® (polyetheretherketone), Insertion device – stainless steel shaft with ABS and polycarbonate handle. Non-absorbable suture(s) with attached stainless steel needles.

Non-absorbable suture options:

- White – braided, uncoated, UHMW polyethylene
- White/blue – braided, uncoated, UHMW polyethylene with monofilament polypropylene cobraid
- White/black – braided, uncoated, UHMW polyethylene with monofilament nylon cobraid,
- Braided, silicone, or PTFE-impregnated polyester (USP), non-absorbable

8.4 FOOTPRINT ULTRA PK SL SUTURE ANCHOR

The Smith & Nephew FOOTPRINT ULTRA PK SL (PEEK-OPTIMA® from Invibio®) Suture Anchor is non-absorbable, attached to an insertion device, and available in 4.5 mm and 5.5 mm. The suture anchor is intended to provide secure reattachment of soft tissue to bone. Attachment of the soft tissue is performed by the surgeon’s preferred technique.

- Non-absorbable suture options PEEK-OPTIMA® from Invibio®

CONFIDENTIAL AND PROPRIETARY

This document contains information that is confidential and proprietary to Smith & Nephew PLC and Smith & Nephew, Inc. and is intended for use only by Smith & Nephew and its manufacturer. It shall not be reproduced or copied in whole or in part, nor shall the contents be disclosed by any means without prior written permission from Smith & Nephew, nor shall anyone make any use of it that is contrary to the expressed or implied wishes of Smith & Nephew.

Study Protocol—Device	
Safety and Performance of PEEK Anchors (DYNOMITE°, SPYROMITE°, RAPTORMITE°, FOOTPRINT° ULTRA PK SL) in Extremities	Number: 2018.15.SMD.PEEK.RET.EXT
	Version: 2.0 05Dec2018
	Page: Page 19 of 54

- Suture (USP #2-0).
- Retention suture- braided polyester non-absorbable suture (USP #2-0).

Table 3 demonstrates the model, and product description of the devices. Refer to individual suture anchor product labels for suture size, type, and quantity.

Table 3: Product Specification, structural composition and description

Product #	72201806	72201881	72201882	72203776 72203783
Specification	RAPTORMITE° 3.0 PK W/NDL, 2 0 ULTRABRA	DYNOMITE° 2.0 PK W/NDL,1 2-0 ULTRABRAID	SPYROMITE° 2.0 PK W/1 2-0 ULTRABRAID WH	FOOTPRINT ULTRA PK SUTURE ANCH SL
Diagram				
Product description	3.0 mm diameter PEEK-OPTIMA® from Invibio® suture anchor	2.0 mm diameter PEEK- OPTIMA® from Invibio® suture anchor	2.0 mm diameter PEEK- OPTIMA® from Invibio® suture anchor	4.5 mm and 5.5 mm PEEK-OPTIMA® from Invibio® suture anchor

8.5 INDICATIONS FOR USE

The following Table 4 identifies the Indications for Use for the Smith & Nephew PEEK Suture Anchors.

CONFIDENTIAL AND PROPRIETARY

This document contains information that is confidential and proprietary to Smith & Nephew PLC and Smith & Nephew, Inc. and is intended for use only by Smith & Nephew and its manufacturer. It shall not be reproduced or copied in whole or in part, nor shall the contents be disclosed by any means without prior written permission from Smith & Nephew, nor shall anyone make any use of it that is contrary to the expressed or implied wishes of Smith & Nephew.

Study Protocol—Device	
Safety and Performance of PEEK Anchors (DYNOMITE°, SPYROMITE°, RAPTORMITE°, FOOTPRINT° ULTRA PK SL) in Extremities	Number: 2018.15.SMD.PEEK.RET.EXT
	Version: 2.0 05Dec2018
	Page: Page 20 of 54

Table 4: Summary of indications for PEEK Anchors (DYNOMITE°, SPYROMITE°, RAPTORMITE°, FOOTPRINT° ULTRA PK SL) in extremities

	DYNOMITE°	RAPTORMITE°	SPYROMITE°	FOOTPRINT° ULTRA PK SL
Foot & Ankle				
Hallux valgus repairs	X	X	X	X
Medial or lateral instability repairs/reconstructions	X	X	X	X
Achilles tendon repairs/reconstructions	X	X	X	X
Midfoot reconstructions	X	X	X	X
Metatarsal ligament/tendon repairs/reconstructions	X	X	X	X
Bunionectomy	X	X	X	N/A
Elbow, Wrist & Hand				
Scapholunate ligament reconstructions	X	N/A	X	N/A
Ulnar or radial collateral ligament reconstructions	X	X	X	N/A
Lateral epicondylitis repair	X	X	X	N/A
Biceps tendon reattachment	X	X	X	N/A

8.6 PRODUCT USE

All study related procedures using the PEEK suture anchors in the extremities have been performed according to the recommended surgical technique described in the labelling and the instructions for use.

CONFIDENTIAL AND PROPRIETARY

This document contains information that is confidential and proprietary to Smith & Nephew PLC and Smith & Nephew, Inc. and is intended for use only by Smith & Nephew and its manufacturer. It shall not be reproduced or copied in whole or in part, nor shall the contents be disclosed by any means without prior written permission from Smith & Nephew, nor shall anyone make any use of it that is contrary to the expressed or implied wishes of Smith & Nephew.

Study Protocol—Device	
Safety and Performance of PEEK Anchors (DYNOMITE [®] , SPYROMITE [®] , RAPTORMITE [®] , FOOTPRINT [®] ULTRA PK SL) in Extremities	Number: 2018.15.SMD.PEEK.RET.EXT
	Version: 2.0 05Dec2018
	Page: Page 21 of 54

8.7 SURGICAL TECHNIQUE

The operative visit of this study is retrospective. The use of the PEEK Anchors (DYNOMITE[®], SPYROMITE[®], RAPTORMITE[®], FOOTPRINT[®] ULTRA PK SL) in extremities was performed per standard of care at the participating study sites.

9. SUBJECT ENROLLMENT AND WITHDRAWAL

Investigators will screen all subjects that have undergone usage of the PEEK suture anchors in the extremities using only the existing information in the medical records.

Investigators will conduct a chart review after IRB approval has been granted. All subjects whose chart undergoes the screening process will be documented on a Screening and Enrollment Log, with the reason for exclusion noted, if applicable. The Investigator or designee must notify the Sponsor upon subject enrollment.

9.1 SUBJECT POPULATION

To minimize the potential for selection bias, Investigators will screen and subsequently enroll subjects (after fulfilling all inclusion and exclusion criteria) on whom PEEK Anchors RAPTORMITE[®], DYNOMITE[®], SPYROMITE[®] and FOOTPRINT[®] ULTRA PK SL in the extremities were implanted. Enrollment will be in sequential order based on the date of their surgical procedure with the investigational device, i.e. earliest to latest.

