5.2 STUDY PURPOSE

This is a retrospective study to evaluate intra-operative, 6 months and 12 months safety and performance of the PEEK anchors (DYNOMITE°, SPYROMITE°, RAPTORMITE°, FOOTPRINT° ULTRA PK SL) for extremities to meet existing MDD/MEDDEV requirements.

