9.2 INCLUSION CRITERIA

Subjects will be considered qualified for enrollment if they meet the following criteria:

- | |
|---|
| 
 1. Subjects who have undergone extremity joint repair using the study devices. 2. Subjects aged 18 years and older at the time of surgery. |
|---|

CONFIDENTIAL AND PROPRIETARY

This document contains information that is confidential and proprietary to Smith & Nephew PLC and Smith & Nephew, Inc. and is intended for use only by Smith & Nephew and its manufacturer. It shall not be reproduced or copied in whole or in part, nor shall the contents be disclosed by any means without prior written permission from Smith & Nephew, nor shall anyone make any use of it that is contrary to the expressed or implied wishes of Smith & Nephew.

Study Protocol—Device	
Safety and Performance of PEEK Anchors (DYNOMITE [°] , SPYROMITE [°] , RAPTORMITE [°] , FOOTPRINT [°] ULTRA PK SL) in Extremities	Number: 2018.15.SMD.PEEK.RET.EXT
	Version: 2.0 05Dec2018
	Page: Page 22 of 54

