9.3 EXCLUSION CRITERIA

Any one (1) of the following criteria will disqualify a potential subject from participation in the study:

1. Subject is entered in another investigational drug, biologic, or device study or has been treated with an investigational product within 12 months post-operative.
2. Subjects who are < 3 months post-operative.

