10.2.3 Safety Endpoints

Safety endpoints include the collection of the following events from the subjects' medical record:

CONFIDENTIAL AND PROPRIETARY

This document contains information that is confidential and proprietary to Smith & Nephew PLC and Smith & Nephew, Inc. and is intended for use only by Smith & Nephew and its manufacturer. It shall not be reproduced or copied in whole or in part, nor shall the contents be disclosed by any means without prior written permission from Smith & Nephew, nor shall anyone make any use of it that is contrary to the expressed or implied wishes of Smith & Nephew.

Study Protocol—Device	
Safety and Performance of PEEK Anchors (DYNOMITE [°] , SPYROMITE [°] , RAPTORMITE [°] , FOOTPRINT [°] ULTRA PK SL) in Extremities	Number: 2018.15.SMD.PEEK.RET.EXT
	Version: 2.0 05Dec2018
	Page: Page 26 of 54

- All adverse events (AEs) and complications occurring from the time of subject enrollment until study termination or study completion including intra-operative adverse events and complications.
- Device related re-intervention.
- Device deficiency.

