12.2 ANALYSIS POPULATIONS

The following analysis populations will be used for this study:

- **Safety Population (SAF):** This includes all subjects who enroll in the study who had previously undergone repair in the extremities using any of the PEEK anchors: RAPTORMITE[°], DYNOMITE[°], SPYROMITE and FOOTPRINT[°] ULTRA PK SL.
- **Per-Protocol Population (PP):** This includes all subjects in the Safety Population, who have no significant protocol deviations and who meet all the inclusion/exclusion criteria. Deviations considered as significant will be defined and finalized prior to database lock.

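### Section 9.1 enrols on implantation while sections 9, 9.2 and 12.2 speak of use, so a subject whose only study anchor failed at insertion can be left out of a study with an intra-operative purpose

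*Combined protocol and SAP*

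**What the plan says.** The combined protocol describes its population in four places, and the words differ.

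- Section 9 sets the screening frame: "Investigators will screen all subjects that have undergone usage of the PEEK suture anchors in the extremities".
- Section 9.1 says that investigators will screen and then enrol, once all criteria are fulfilled, subjects on whom the anchors are described thus: "SPYROMITE[®] and FOOTPRINT[®] ULTRA PK SL in the extremities were implanted". The stated reason is to limit selection bias.
- Section 9.2, criterion 1 (repeated in the synopsis): "Subjects who have undergone extremity joint repair using the study devices".
- Section 12.2 defines the safety population as enrolled subjects "who had previously undergone repair in the extremities using any of the PEEK anchors". The per-protocol population is a subset of it.

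The intra-operative question is explicit. Section 5.2 says: "This is a retrospective study to evaluate intra-operative, 6 months and 12 months safety and performance of the PEEK anchors". Section 10.2.3 collects adverse events "including intra-operative adverse events and complications", and also device deficiency. Section 14.1.6 counts malfunctions and use errors as deficiencies, and section 11.1 collects events and deficiencies from the time of surgery.

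No section says what to do with an anchor that was tried and not retained.

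**The concern.** An anchor that breaks, will not deploy or pulls out at insertion is the most direct intra-operative performance failure the study could observe. If the surgeon then finishes with a non-study device, the subject leaves the operation with no study anchor implanted. A site that applies 9.1 as written would not enrol that subject.

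The loss would be one-sided, because only device failures can leave by this route. It would also be invisible in the analysis. Section 12.3 uses the per-protocol population for the primary analysis and the safety population for sensitivity, and both contain only enrolled subjects. With up to 15 sites and no rule, sites may also decide differently, so per-anchor rates could partly reflect how each site read the word *implanted*.

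**Working it through.** **Step 1. Which cases are at risk.** Take each outcome of a failed insertion and apply the two wordings.

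| What happened | 9.1 (*implanted*) | 9, 9.2, 12.2 (*usage*, *using*) |
|---|---|---|
| Failed anchor replaced by the same or another study anchor | Enters | Enters |
| Several study anchors, one failed, others retained | Enters | Enters |
| Only study anchor failed, repair finished with a non-study device | Omitted on a literal reading | Can be read to admit |

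Only the third row is ambiguous. Section 9.3 does not settle it: of its two exclusions, one concerns other investigational studies or products and the other is "Subjects who are < 3 months post-operative". Section 9.6 does not settle it either. It treats a subject as enrolled once the criteria and consent or waiver are satisfied, and does not mention implantation.

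**Step 2. Direction.** Let *n* subjects be enrolled, *s* of them successes and *d* with a device deficiency. Suppose *k* third-row cases are omitted, each with a deficiency and each counted as not a success.

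- Success: *s/n* as reported against *s/(n+k)* among all attempted. The reported rate is higher for any *k* > 0 (with *s* > 0).
- Deficiency: *d/n* as reported against *(d+k)/(n+k)*. The reported rate is lower whenever *d* < *n*.

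The direction is therefore fixed, given those two assumptions. A malfunction is a deficiency under 14.1.6. Whether an intra-operative exchange is a failure of the primary endpoint is not stated: section 10.2.1 defines success at 6 months by absence of signs of device failure and/or re-intervention.

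**Step 3. The plan's own figure.** The only rate available is the 91% success assumed in section 13. That section's lower probability of 15.2% at 20 subjects reproduces as 0.91^20 = 0.1516, the chance of 20 successes in 20. With 19/20 the exact interval is 0.7513 to 0.9987, a half-width of 0.1237, wider than the 0.11 between 91% and 80%. At 120 subjects the half-width condition is met with probability about 1.00, consistent with the stated >95%. These figures concern precision and do not bear on who is eligible. Only the 91% is carried forward.

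**Step 4. Illustration of size.** The documents give no insertion-failure rate. Let *q* = *k/(n+k)* be the share of attempted cases in the third row, with an assumed range of 1% to 10%. Then success among all attempted = 0.91 × (1 − *q*), and cases omitted per *n* enrolled = *n* × *q*/(1 − *q*).

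| *q* (assumed) | Success among attempted | Overstatement, points | Omitted per 80 enrolled | Omitted per 480 enrolled |
|---|---|---|---|---|
| 1% | 90.1% | 0.9 | 0.8 | 4.8 |
| 2% | 89.2% | 1.8 | 1.6 | 9.8 |
| 5% | 86.45% | 4.55 | 4.2 | 25.3 |
| 10% | 81.9% | 9.1 | 8.9 | 53.3 |

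**Step 5. One case at the per-anchor minimum.** With 20 enrolled for an anchor and one omitted failure, 18/20 = 90.0% becomes 18/21 = 85.7%. A deficiency rate of 0/20 = 0% becomes 1/21 = 4.8%.

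**The case against.** The strongest reply is that 9.1 is not the operative gate. Section 9.2 lists what qualifies a subject, and it asks for repair using the devices. No exclusion bars an insertion failure, 9.6 adds no implantation condition, and screening covers all usage with reasons for exclusion logged. On that view *implanted* is loose drafting.

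This stands in part. A reader might infer from 9.1 that enrolment is strictly confined to implanted subjects and that insertion failures never enter. The documents do not support that, because the wider wording is also there and most insertion failures (the first two rows of the table) enter under either wording. Three other inferences also go too far:

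- That 9.2 and 12.2 demand a completed repair with the study anchor. Neither says so.
- That a subject switched to another study anchor counts only under the replacement. The plan has no rule assigning subjects to anchors.
- That the intra-operative purpose cannot be answered. Events and deficiencies in every enrolled subject are collected from surgery onward, and operative notes are reviewed.

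The reply does not remove the conflict. Section 9.1 is the passage that describes whom sites enrol, and it presents the inclusion and exclusion criteria as conditions to be met by subjects in whom anchors were implanted. A repair finished with a non-study device is also not plainly a repair using the study devices, so 9.2 does not clearly rescue the case. The screening log helps only if the chart was found, and it feeds no analysis.

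**Conclusion.** The point holds as an inconsistency and a missing rule. Under a literal reading of 9.1, subjects whose only study anchor failed at insertion and was replaced by a non-study device can be left out. Their omission would push the deficiency rate down and, if such cases count as device failures, the success rate up. The sensitivity analysis could not show it.

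The size is unknown. The 0.9 to 9.1 points above rest on three assumptions: an insertion-failure share that the documents do not give, 91% success among those enrolled, and every omitted case counting as a failure. A reader might take that range as an estimate of bias, but it only illustrates how the rate would move. The effect of a single case matters most near the minimum of 20 per anchor. This is worth correcting because the correction is cheap, not because a large bias has been shown.

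**What to change.** Use one wording in 9.1, 9.2, the synopsis criterion and 12.2 that admits every subject in whom a study anchor was used or its placement attempted, whether or not it was retained. State briefly what counts as an attempt, so that sites apply it alike.

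Record insertion failures as device deficiencies in the safety population under the anchor that failed. Report the success rate twice: with attempted-but-not-retained cases counted as device failures, and among implanted subjects only. Fix before enrolment which of the two is the headline rate. That is a legitimate choice for the sponsor, and either can be defended if it is made in advance.

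The cost is wording in those four places and a matching sentence in the primary endpoint and its analysis (10.2.1 and 12.3). Section 23.1.3 says version 2.0 takes effect before enrolment, so the change fits best before the first subject is enrolled. Operative notes are already reviewed under 11.1. The downsides are a wider record search, because implant records alone will not find these cases, some poorly documented attempts, and a possibly slightly lower success rate.

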9.2 INCLUSION CRITERIA

Subjects will be considered qualified for enrollment if they meet the following criteria:

- | |
|---|
| 
 1. Subjects who have undergone extremity joint repair using the study devices. 2. Subjects aged 18 years and older at the time of surgery. |
|---|

CONFIDENTIAL AND PROPRIETARY

This document contains information that is confidential and proprietary to Smith & Nephew PLC and Smith & Nephew, Inc. and is intended for use only by Smith & Nephew and its manufacturer. It shall not be reproduced or copied in whole or in part, nor shall the contents be disclosed by any means without prior written permission from Smith & Nephew, nor shall anyone make any use of it that is contrary to the expressed or implied wishes of Smith & Nephew.

Study Protocol—Device	
Safety and Performance of PEEK Anchors (DYNOMITE [°] , SPYROMITE [°] , RAPTORMITE [°] , FOOTPRINT [°] ULTRA PK SL) in Extremities	Number: 2018.15.SMD.PEEK.RET.EXT
	Version: 2.0 05Dec2018
	Page: Page 22 of 54

